### **3.1.2 Follow Up Phase**

There is no follow-up period for the study.

## **3.2 Study Endpoints**

### **3.2.1 Primary Study Endpoints**

The primary objectives are descriptive and designed as a feasibility study. Descriptive data will be collected on the following:

- Assessing for subject comfort and tolerability of the DOVE device

- Documenting subject comfort and subjective participant opinions of device wearability

### **3.2.2 Secondary Study Endpoints**

Evaluate community availability status quo of opioid overdose reversal agents in study participant population.

- Evaluate severity and prevalence of opioid overdoses within study participant population.
- Assess frequency of opioid overdose.

## **4 Study Population and Duration of Participation**

### **4.1 Inclusion Criteria**

- Males and Females
- 21 years of age or older
- Have used opioids for more than 3 months or will be having surgery where opioids will be administered.
- Able to provide informed consent
- Moderate to severe chronic pain treated (by prescription or illicitly) with opioids or recreation use

### **4.2 Exclusion Criteria**

- Pregnant

### **4.3 Subject Recruitment**

Subject recruitment will occur through Penn Medicine Faculty engagement, particularly referrals from Penn physicians. The study staff will send emails to Penn Medicine physicians, asking them to refer subjects to study personnel for contact during recruitment and/or seeking permission to contact study participant identified through screening. We also plan to use IRB-approved advertisements targeting the Delaware Valley region. All ads will be submitted for IRB approval prior to use. Subjects may also be recruited from PennSeek and Pennomics. We will seek permission to contact from their physicians to approach the patient for recruitment into the study. If the physician does not respond, the study team will send the patient an IRB-approved recruitment letter and follow up with a phone call at least one week after.

### **4.4 Duration of Study Participation**

Total duration of study participation for enrolled subjects will be approximately 2-3 hours per visit for each of the parts.

### **4.5 Total Number of Subjects and Sites**

For Part 1 and 2, up to 150 subjects will be enrolled.

**Part 1:** Enrollment of approximately 100 subjects.

**Part 2:** Enrollment of approximately 50 subjects.

Subjects enrolled in Part 1 will be asked if they are interested in participating in part 2 but will need to again go through screening and enrollment.

#### **4.6 Vulnerable Populations:**

No vulnerable populations will be used in this study.

### **5 Study design phase**

#### **5.1 Receipt**

For Part 1, all questionnaires will be administered to the subjects by the clinical research team.

For Part 2, the device will be delivered by the manufacturer to the clinical research team. The clinical research team will maintain records logs regarding device dispensing and return devices. This will be in addition to any records kept by the sponsor. The sponsor will maintain the device disposal logs.

#### **5.2 Storage**

The devices and supplies will be stored in a locked room where only study personnel will have access.

#### **5.3 Blinding**

There is no blinding to the study.

#### **5.4 Administration and Accountability**

For Part 2, the prototype of the device study will be given to each subject at the study visit. A product log will be kept in which product reconciliation will be collected at every visit with information on product dispensing, such as: date dispensed, and to which subjects the device was given and returned. A standard form will be utilized to document this information throughout the study period.

#### **5.5 Subject Compliance Monitoring**

For Part 2 subject are only required to wear the device for the duration of the visit.

##### **5.5.1 Return or Destruction of Investigational Product**

The investigational product will be returned to the investigator for continued development at the conclusion of the study visit. Date of return will be logged on the initial reconciliation case report form (CRF). A standard form will be utilized to document the return and destruction of the prototype devices.

### **6 Study Procedures**

#### **Table 1: Schedule of Study Procedures**

Page 9

CONFIDENTIAL

This material is the property of the University of Pennsylvania.

Study Procedures	Part 1		Part 2	
	Screening	Baseline	Screening	Baseline
Number of visits	1	1	1	1-2
Review Inclusion/Exclusion Criteria	X		X	
Informed Consent	X		X	
Demographics/Medical History	X		X	
Questionnaire		X		X
Prior/Concomitant Medications	X	X	X	X
Dispense Investigational Product				X
Collect Investigational Product				X
Assessment of possible AE				X

### **6.1.1 Screening (Parts 1 and 2)**

- Review of Inclusion/Exclusion criteria

### **6.1.2 Baseline Visit**

- Signed informed consent
- Review of demographics, medical history and medications
- Questionnaire
- Dispense Investigational Product (only Part 2)
- Collect Investigational Product (only Part 2)
- Assessment of possible Adverse Events (only Part 2)

### **6.2 Follow Up Phase of the Study**

There will be no additional follow-up visit after completion of the study.

### **6.3 Subject Withdrawal**

Early withdrawal from the protocol poses no safety risk to participating subjects. The study participant may choose to withdraw at any point while participating in the protocol without impact to their care. They may also be discontinued from the study at the discretion of the Investigator for lack of adherence to the protocol, safety concerns, or study termination.

### **6.4 Data Collection and Follow-up for Withdrawn Subjects**

There is no need for follow-up for subjects who complete or withdraw from the study.

## **7 Study Evaluations and Measurements**

### **7.1 Medical Record Review**

- Date of birth & Demographics
- Medications
- Medical/surgical history
- Information related to opioid use and history of overdose
- EPIC chart review to ensure subject meets inclusion criteria or does not meet exclusion criteria.

### **7.2 Pregnancy Testing**

There will not be any pregnancy test. Study participant will be asked if they are pregnant or not.

### **7.3 Laboratory Evaluations**

There will not be any laboratory evaluations.

### **7.4 Other Evaluations, Measures**

Part 1- Questionnaire will be given to subjects once they have been consented.

Part 2 - Participants will also be surveyed/interviewed for their subjective experience with the DOVE prototype device. The interview and questionnaire will ensure that key topics are covered, while also allowing the subject to discuss issues and experiences with the prototype device that the investigational team has not considered.

### **7.5 Safety Evaluations**

The principal investigator will be responsible for evaluating and maintaining the highest safety standards and practices. For the purposes of this trial, there will not be a DSMB. Any adverse device events will be reported to the principal investigator and sponsor.

## **8 Statistical Plan**

Survey answers will be entered into a RedCap database and responses will be aggregated and summarized using descriptive statistics. To compare differences survey responses among study participant subgroups, we will use t-tests or Wilcoxon rank-sum tests (F-tests or Kruskal-Wallis test) for continuous variables and Pearson chi square tests or Fishers exact tests for categorical variables. Linear and logistic regression will be used to assess for differences in the continuous and dichotomous outcomes, respectively. All hypothesis tests will be two-sided using a two-sided alpha of 0.05 as our threshold for statistical significance. We will use Stata and/or SAS to analyze the data.

## **8.1 Primary Endpoint**

For part 1 and 2 the primary objective is qualitative, only descriptive information will be obtained. The endpoint will be collection of feasibility and safety data.

As the primary objectives are descriptive and designed as a feasibility study, no power analysis will be performed. The sample size is one of convenience and limited by resources.

## **8.2 Secondary Endpoints**

Evaluate community availability status quo of opioid overdose reversal agents in study participant population.

- Evaluate severity and prevalence of opioid overdoses within study participant population.
- Assess frequency of opioid overdose.
- Assess frequency of opioid overdose.

## **8.3 Sample Size and Power Determination**

As the primary objectives are descriptive and designed as a feasibility study, no power analysis will be performed. The sample size is one of convenience and limited by resources.

## **8.4 Statistical Methods**

For the primary objective, qualitative data will be analyzed with descriptive charts and discussion. The secondary objective and other continuous variables will be analyzed by descriptive and inferential statistics.

Survey answers will be entered into a RedCap database and responses will be aggregated and summarized using descriptive statistics. To compare differences survey responses among study participant subgroups, we will use t-tests or Wilcoxon rank-sum tests (F-tests or Kruskal-Wallis test) for continuous variables and Pearson chi square tests or Fishers exact tests for categorical variables. Linear and logistic regression will be used to assess for differences in the continuous and dichotomous outcomes, respectively. All hypothesis tests will be two-sided using a two-sided alpha of 0.05 as our threshold for statistical significance. We will use Stata and/or SAS to analyze the data.

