## **2 Study Objectives**

### **2.1 Primary Objective**

The primary objective of Part 1 is to determine the opioid user population's need for a wearable device that will treat an opioid overdose. The primary objective of Part 2 is to obtain descriptive data and functional data on DOVE device prototypes. Naloxone will not be administered during the trial. Examples of data collected are:

- Study participant will be asked about their opioid use and overdose history.
- Accessibility to Naloxone.
- Study participant will be asked to evaluate potential wearable device designs (Part 2 only).
- Study participant evaluates which devices would be more helpful in terms of detection and comfort (Part 2 only).

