### **2.2 Secondary Objectives**

The secondary object of Part 1 is to evaluate community availability status quo of opioid overdose reversal agents in study participant population.

- Evaluate severity and prevalence of opioid overdoses within study participant population.
- Assess frequency of opioid overdose.

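### Does the missing recall window for overdose frequency invalidate the planned subgroup tests?

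*Combined protocol and SAP*

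**What the plan says.** The secondary objective belongs to Part 1 (about 100 subjects, section 4.5). Section 8.2 lists "Assess frequency of opioid overdose" as a secondary endpoint, and section 2.2 adds "Evaluate severity and prevalence of opioid overdoses within study participant population". None of these entries gives a period, a unit or a denominator.

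The data are retrospective. Section 2.1 states "Study participant will be asked about their opioid use and overdose history", and the chart review in section 7.1 covers "Information related to opioid use and history of overdose". Part 1 is a single questionnaire (section 3.1), and the Follow Up Phase entry reads "There is no follow-up period for the study".

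Eligibility (section 4.1) includes "Have used opioids for more than 3 months or will be having surgery where opioids will be administered". Past use can therefore run from none, for some surgical patients, to many years.

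For analysis, section 8.4 says "The secondary objective and other continuous variables will be analyzed by descriptive and inferential statistics". It names t-tests or Wilcoxon tests, their several-group counterparts, and chi-square or Fisher tests. It then adds "Linear and logistic regression will be used to assess for differences in the continuous and dichotomous outcomes, respectively". It names no subgroup, covariate or exposure term. Sections 8.1 and 8.3 state that there is no power analysis and that the sample is one of convenience.

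**The concern.** A frequency needs a period. If the survey asks how many overdoses a person has ever had, the answer mixes how often that person overdoses with how long the person has used opioids. Two subgroups with the same yearly rate but different lengths of use then differ in both the count and the proportion who have ever overdosed. Using Wilcoxon in place of the t-test, or chi-square on a yes/no version, does not help, because the mixing is in the outcome and not in the test.

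A significant result could then be read as showing that one subgroup is at higher current risk, when its members may only have used opioids for longer. Part 1 asks who needs a wearable device, so such a misreading would matter. Section 8.4 sends these data to tests at 0.05 and names no adjustment, so the plan appears to invite it.

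**Working it through.** **Inputs from the documents.** Part 1 has about 100 subjects (4.5); tests are two-sided at 0.05 (8.4); use is more than 3 months with no upper limit, or surgery is planned (4.1). The documents give no overdose rate, length of use, subgroup or effect size, so there is no planned figure to reproduce.

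**Assumptions.** Two subgroups of 50; the same yearly rate, 0.1 or 0.2; years of use gamma-distributed (shape 2, minimum 0.25); overdispersed Poisson counts; 2,000 runs per setting. The Monte Carlo standard error near 5% is √(0.05 × 0.95 / 2000) ≈ 0.5 points.

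**Step 1: mechanism.** Expected lifetime count = rate × years. At 0.1 per year, 10 vs 5 mean years gives 1.0 vs 0.5. The ratio is 10/5 = 2 whatever the rate.

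For ever having overdosed, with fixed years and no overdispersion, the proportion is 1 − exp(−rate × years). At 0.1 per year, 3 vs 6 years gives 1 − exp(−0.3) = 25.9% and 1 − exp(−0.6) = 45.1%. With 50 per group, a two-proportion test is significant about 52% of the time.

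**Step 2: unadjusted lifetime outcomes, same rate of 0.1.** Percentage of runs with p < 0.05:

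| Mean years | t-test, count | Wilcoxon, count | Logistic, ever overdosed |
|---|---|---|---|
| 5 vs 5 | 3.6 | 5.1 | 4.8 |
| 6 vs 5 | 6.6 | 6.2 | 5.2 |
| 7 vs 5 | 13.1 | 12.0 | 10.7 |
| 10 vs 5 | 43.0 | 38.0 | 31.3 |
| 10 vs 3 | 82.0 | 77.6 | 69.2 |

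Large distortion needs a twofold or greater gap in mean years between subgroups that the plan does not name.

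**Step 3: the planned tests on a 12-month count.**

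| Mean years | Rate per year | t-test | Wilcoxon |
|---|---|---|---|
| 10 vs 5 | 0.1 | 5.2 | 5.4 |
| 10 vs 3 | 0.1 | 4.0 | 4.6 |
| 10 vs 5 | 0.2 | 4.1 | 4.2 |
| 10 vs 3 | 0.2 | 5.4 | 5.7 |

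Nothing needs correcting here. Robust Poisson regression on the same data gives 4.2% to 5.5%, so a count model shows no gain in error control.

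**Step 4: the planned regressions on lifetime outcomes, constant rate of 0.1.** In the order of the table in step 2:

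- Linear regression with years of use as a covariate: 4.7, 5.0, 4.1, 3.6 and 5.1%.
- Logistic regression for ever overdosed, with log years: 5.0, 3.8, 4.2, 4.7 and 5.5%.
- Robust Poisson regression with log years as an estimated covariate: 6.2, 6.5, 5.8, 6.8 and 7.6%, no better than the planned methods.

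**Step 5: cost of a short window.** At 0.1 to 0.2 per year, 100 subjects give 100 × 0.1 = 10 to 100 × 0.2 = 20 events in 12 months. At 5 mean years of use, lifetime events number 50 to 100. For a true doubling (0.1 vs 0.2, equal years), power is about 44% on lifetime counts and about 21% on the 12-month count.

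**Step 6: a falling rate.** Suppose the rate starts at 0.2 and falls 20% per year of use. At 10 vs 5 and 10 vs 3 mean years, the unadjusted t-test rejects 14% and 35%. A fixed log-years offset rejects 23% and 42%, which is worse. Log years as an estimated covariate in a robust Poisson model gives 7% and 7%. The linear model in step 4 was checked only at a constant rate.

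**The case for a change.** The best case for a change is that it is cheap and can only be made early. An endpoint called frequency is undefined without a period. The documents do not show that length of use is recorded as a duration, and at a single contact an unasked question may not be recoverable. Section 19 foresees possible publication, and the authors chose significance tests. The direction of the distortion does not depend on the assumed rates.

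Much of this stands. The text gives no window and names no covariate, and stating both would make the report easier to read. A lifetime comparison made without adjustment and reported as a difference in risk would be wrong.

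It does not show that the plan leads there. The recall period belongs in the questionnaire, which is not among the documents, and a fixed period there removes the problem. Opioid use is asked about and reviewed in the chart, and eligibility requires judging whether use exceeds 3 months, so the material for a duration variable is probably at hand. The regressions in section 8.4 can take it. If duration proves unavailable, a lifetime comparison is still valid as a comparison of lifetime burden: a t-test that rejects equal lifetime means when they differ makes no error, and only the reading can go wrong. The question of device need is also a primary objective, analysed descriptively under sections 8.1 and 8.4, and not by these tests.

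**Conclusion.** No change follows. The observation is accurate: sections 8.2 and 8.4 give no look-back period, unit or time at risk for overdose frequency. The harm is conditional. It needs a lifetime question, subgroups whose lengths of use differ widely, no adjustment, and a report that reads burden as rate. Under the assumed inputs, unadjusted t-test rejection at equal rates runs from 7% (6 vs 5 mean years) to 82% (10 vs 3). It returns to about 5% with a 12-month count, or with years of use in the planned linear regression when the rate is constant.

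The choice of window is a fair trade-off, since the short one roughly halves power for a doubled rate, and a count model corrects no error seen in the windowed data. What remains is detail that a competent analyst supplies: report the period the questionnaire used, adjust lifetime outcomes for length of use or label them as lifetime burden, and describe people with no prior use separately. For a secondary endpoint in a convenience-sample pilot, that is enough. All the percentages rest on assumed rates, lengths of use and group sizes.

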## **19 Publication Plan**

The PI and the research team will have complete access to the data collected.

**Part 1** is currently designed for exploratory work but publication could come from it. This part is intended for baseline data on device design and population needs.

**Part 2** may lead to publication. This part is intended for baseline data on the device.

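### Subgroups and tests are neither named nor counted, yet every two-sided p<0.05 counts as statistically significant, with no error control and no exploratory label on the p-values

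*Combined protocol and SAP*

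**What the plan says.** Section 8.4 divides the analysis in two. On the descriptive side: "For the primary objective, qualitative data will be analyzed with descriptive charts and discussion". On the inferential side: "The secondary objective and other continuous variables will be analyzed by descriptive and inferential statistics".

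The inferential methods follow: "To compare differences survey responses among study participant subgroups, we will use t-tests or Wilcoxon rank-sum tests (F-tests or Kruskal-Wallis test) for continuous variables", with chi-square or Fisher's exact tests for categorical variables. Regression is added: "Linear and logistic regression will be used to assess for differences in the continuous and dichotomous outcomes, respectively". One decision rule covers all of it: "All hypothesis tests will be two-sided using a two-sided alpha of 0.05 as our threshold for statistical significance". Section 8 and the Statistical Methodology row of the Study Summary carry the same paragraph.

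Section 8.3 gives no planned effect or power: "As the primary objectives are descriptive and designed as a feasibility study, no power analysis will be performed". Section 3.1 describes both parts as exploratory. Section 19 says that Part 1 "is currently designed for exploratory work but publication could come from it", and that Part 2 may also be published.

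No section names the subgroups, lists the responses to be compared, names regression covariates, counts the tests, or says how the p-values are to be read as a set.

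**The concern.** An error rate of 0.05 per test says little about a set of tests whose size is unknown. The plan leaves open which responses are compared and across which subgroups, and that choice can be made after the data are seen. It then attaches a formal significance claim to each result.

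The exploratory label belongs to the study, not to the tests. Nothing in Sections 8 or 8.4 tells a reader of a published subgroup difference that it was one of an unstated number of looks.

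At stake are the study's only inferential results: those on the secondary objective (availability of reversal agents; severity, prevalence and frequency of overdose) and the subgroup contrasts.

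**Working it through.** **Inputs from the documents.** Two-sided alpha of 0.05 for every test (Sections 8, 8.4 and the Study Summary). About 100 subjects in Part 1 and about 50 in Part 2 (Section 4.5). There is no power calculation or family-wise error rate to reproduce. The only stated error rate is the per-test one, and for a single test 1 − 0.95 = 5%.

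**Assumption.** The number of tests, k, is not in the documents, so it is varied.

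**Step 1: independent tests, no true differences.** Chance of at least one p<0.05 = 1 − 0.95^k. Expected number of false results = 0.05 × k, whatever the correlation.

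**Step 2: correlated tests.** Answers from the same person tend to be correlated. The two correlation columns come from simulating k test statistics as normal variables with a common correlation (100,000 replicates).

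| k | Independent | Correlation 0.3 | Correlation 0.5 | Expected false results |
|---|---|---|---|---|
| 5 | 22.6% | 20.9% | 18.4% | 0.25 |
| 10 | 40.1% | 35.1% | 28.8% | 0.50 |
| 14 | 51.2% | 43.9% | 35.0% | 0.70 |
| 20 | 64.2% | 54.1% | 42.1% | 1.00 |
| 40 | 87.1% | 74.6% | 57.2% | 2.00 |

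**Step 3: where the chance passes one half.** With independent tests, k must exceed ln 0.5 / ln 0.95 = 13.5, so 14 tests are needed; at 13 the chance is 48.7%. Fourteen tests would be, for example, 7 responses by 2 subgroup factors. With correlated statistics the number needed is about 14 at correlation 0.1, 18 at 0.3, 30 at 0.5 and 100 at 0.7.

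**Step 4: categorical items.** Fisher's exact test rejects less often than its nominal level. Its actual size s was computed exactly for response rates of 10% to 50%, and the number of independent tests needed to pass one half is ln 0.5 / ln(1 − s), rounded up.

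- 50 versus 50 subjects: s = 1.8% to 3.5%, so 39 down to 20 tests.
- 70 versus 30 subjects: s = 2.4% to 4.0%, so 29 down to 18 tests.
- 25 versus 25 subjects (all of Part 2): s = 0.9% to 3.3%, so 79 down to 21 tests.

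**Reading.** At any k above 1 the chance of a false significant result exceeds 5% for independent tests run at full nominal size. How far it exceeds 5% cannot be settled from the documents.

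**The case against.** This is a pilot with a convenience sample. Its primary objective is descriptive (Sections 8.1 and 8.4), and both parts are openly exploratory. Many statisticians would not require adjustment in such a survey, and a per-test 0.05 is not confirmatory in itself. Part 1 is a single brief questionnaire (Section 3.1) and the secondary endpoints are few, so the number of tests could be small. These points stand. They limit the consequence and make formal adjustment a matter of judgement. They do not withdraw a rule that calls every p<0.05 significant.

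A reader might infer more than the documents support:

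- **That a false significant finding is more likely than not.** This needs about 14 independent tests, or more with correlated answers or Fisher's exact test. The questionnaire is not in the documents, so a count that high is possible but not shown.
- **That every response will be tested in unlimited subgroups.** The plan does not say so. The accurate word is unspecified.
- **That chance findings will steer the device design.** Section 3.1 bases design changes on comfort, fit and design testing and on verbal feedback. No section ties them to subgroup p-values.
- **That the paired tests invite picking the smaller p-value.** The usual meaning is a choice by distribution or cell count. Even always taking the smaller of the t-test and Wilcoxon p-values added only 1 to 6 percentage points in simulations with 100 subjects and 5-point items.

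**Conclusion.** The concern holds in a limited form. The plan applies an unadjusted 0.05 significance rule to a set of subgroup comparisons and regressions that is neither named nor counted, and it does not label those p-values exploratory. With no true differences and independent tests, the chance of at least one false significant claim runs from 23% at 5 tests to 64% at 20, and positive correlation or Fisher's exact test lowers it. These figures rest on an assumed number of tests, which the documents do not give.

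The exposure is confined to secondary and subgroup findings. The descriptive primary results are untouched and no confirmatory conclusion is at risk. The change is still worth making, because it alters what the study may claim in print and costs very little.

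**What to change.** In the Study Summary, Section 8 and Section 8.4, replace the significance sentence with: 'Subgroup comparisons and regressions are exploratory; each is reported as an estimated difference with a 95% confidence interval and nominal p-value, together with the total number of comparisons made, and no difference is declared statistically significant on an unadjusted p-value.'

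Before analysis, list the subgroups and the survey responses to be compared. This is the part that stops the set from being chosen after the data are seen, and any adjustment would depend on it.

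Optionally, if a significance claim is wanted, base it on Benjamini-Hochberg adjusted p-values over that listed family, separately within each part.

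The cost is wording in three places, one short list and, if the option is taken, a line of code. The downside is fewer subgroup results called significant. The loss of power cannot be put in figures because the documents give no effect size. The descriptive analyses do not change.
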